## Specific Aims and Hypotheses

### Specific Aims and Hypotheses

We plan to complete data collection in 25 treatment-seeking AUD patients. Following a brief inpatient lead-in phase to facilitate abstinence, the patients will undergo a pre-DIS fMRI scan using a passive alcohol cue-reactivity paradigm, with high-calorie food cues serving as control stimuli. They will then receive 10 days of outpatient open-label DIS treatment that includes taking DIS 500 mg every other day, with supervised dosing. They will then undergo a post-DIS fMRI scan using the same cue-reactivity task used in the pre-DIS scan. They will then be followed for 30 days while receiving open-label DIS 250 mg daily, with weekly medical management visits that will include monitoring of alcohol use and medication adherence, and administering a supervised dose of DIS 250 mg. During both phases, patients will be repeatedly informed of the risk of the DIS-alcohol reaction.

Aim 1: Measuring the effects of DIS treatment on cue-elicited neural activity: We predict that, from the pre- to the post-DIS fMRI scans, there will be: increased cue-induced activity in the insula, VMPFC and DLPFC; increased cue-induced insula-VS positive functional connectivity; increased cue-induced VMPFC-VS positive connectivity; increased cue-induced DLPFC-VS negative functional connectivity; reduced cue-induced activity in the VS; reduced cue-induced craving; and a stronger relationship between cue-induced VS activity and cue-induced craving. These effects of DIS treatment will be specific to alcohol cues. Furthermore, we predict that the effects of DIS treatment on insula-VS and VMPFC-VS functional

connectivity will be mediated by self-report measures of alcohol incentive salience at the post-DIS scan; and that the effects of DIS treatment on DLPFC-VS negative functional connectivity will be mediated by self-report measures of the perceived likelihood and unpleasantness of the DIS-alcohol reaction at the post-DIS scan.

Aim 2: Using the effects of DIS treatment on cue-elicited neural activity to predict relapse: We predict that individual differences in cue-induced VS activity in the post-DIS fMRI scan will predict relapse during a subsequent 30 days of DIS treatment, after controlling for cue-induced VS activity during the pre-DIS scan. Here, relapse will be defined as any alcohol use during the 30-day DIS treatment period.

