Secondary Aims: (1) We will identify regions across the whole brain in which the effects of 10-day DIS treatment on cue-induced neural activity predict adherence during 30-day DIS treatment. (2) We will identify regions across the whole brain in which the effects of 10-day treatment on cue-induced neural activity predict the decision to continue DIS treatment beyond 30-days. (3) We will acquire baseline measures of AUD severity, alcohol saliency, motivation for change, impulsivity, self-regulation and tolerance for risk, and will examine how these variables moderate the effects of DIS on cue-induced neural activity. (4) If a significant number ( $>1/3$ ) of patients sample alcohol during the 10-day DIS treatment and thus experience the DIS alcohol reaction, we will perform a subgroup analysis comparing how the neural effects of DIS treatment in such patients differ from patients who do not sample DIS during the 10-day treatment. This will allow us to determine whether the neural effects of actually experiencing the DIS-alcohol reaction are different from the effects of mere expectation of the DIS-alcohol reaction.

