Each clinic visit will include the following procedures: an RA will measure vital signs; perform breath alcohol and urine ethyl glucoronide (EtG) testing; obtain self-reports of alcohol use since the previous clinic visit; a physician or a nurse will administer a single dose of disulfiram 500 mg and instruct about the DIS-alcohol reaction, and review for any alcohol use and any adverse effects of disulfiram. At the third clinic visit, a physician will assess for psychiatric symptoms, including administering the HAM-A, HAM-D and CGI; and perform a Treatment Services Review. On the 4th clinic visit (after 10 days of taking DIS 500 mg every other day) patients will complete a number of self-report measures (OCDS, RCQ, AASe). **A blood sample (10cc, or 2 tablespoons) will be obtained for liver functions and CBC on the 4th visit, to determine the presence of any effects of disulfiram on liver function and blood cell counts.** After completing the clinic procedures on the 4th clinic visit, patients will be escorted in a taxi to the MRI facility located at NYSPI for the post-DIS MRI scan. They will then return to the STARS clinic 2 days later to begin the 30-day DIS treatment period.

30-Day DIS Treatment:

After completing the post-DIS MRI scan, patients will be followed for 30 days while continuing DIS treatment. In this phase, they will attend the STARS clinic weekly, for a total of 4 visits. The first weekly visit will occur 2 days after the post-DIS MRI scan. The procedures at each visit will include the following: the RA will measure vital signs; perform Breathalyzer and urine EtG testing; administer TLFB self-report of alcohol use over the previous 7 days; obtain self-report of DIS adherence; and count pills remaining from the previous week. A physician will meet with the patient to monitor for adverse effects of DIS; inquire about alcohol use since the last visit; assess for the presence of depression, psychosis and suicidal ideation; administer the CGI and the TSR; give a single dose of disulfiram 250 mg; dispense a 6-day supply of DIS 250 mg tablets to be taken once daily until the next clinic visit; and instruct about the DIS-alcohol reaction.

Instruction About the DIS-Alcohol Reaction:

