Study: # 7193 entitled NEUROCOGNITIVE MECHANISMS OF DISULFIRAM TREATMENT OF ALCOHOL USE DISORDER

PI: [name], PhD

NCT# NCT02735577

Data Analysis Plan created: November 14, 2014

Data Analysis: Functional images will be pre-processed according to standard procedures. A whole-brain general linear model analysis will examine effects of time-point (pre-DIS vs. post-DIS) and cue-type (alcohol vs. food), as well as interaction effects. Psychophysiological interaction analysis will examine cue-elicited functional connectivity between the VS and its inputs from the insula, VMPFC and DLPFC, and how these are changed from pre- to post-DIS. Statistical mediation analyses will determine the extent to which these changes are mediated by the perceived likelihood and salience of the DIS alcohol reaction. Logistic regression analysis will be used to determine whether post-DIS cue-induced VS activity predicts drinking during 1 month of DIS, after controlling for pre-DIS cue-induced VS activity, as well as for AUD severity, motivation, risk-taking, insight and impulsivity.

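### Aim 2 does not separate relapse after the post-DIS scan from drinking that had already resumed before it

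*Protocol*

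**What the plan says.** Protocol, Specific Aims and Hypotheses, Aim 2: individual differences in VS activity at the post-DIS scan "will predict relapse during a subsequent 30 days of DIS treatment". The one adjustment that Aim 2 names reads "after controlling for cue-induced VS activity during the pre-DIS scan". The outcome is broad: "relapse will be defined as any alcohol use during the 30-day DIS treatment period". The SAP asks by logistic regression "whether post-DIS cue-induced VS activity predicts drinking during 1 month of DIS". Its adjustment goes further than the protocol's and reads "after controlling for pre-DIS cue-induced VS activity, as well as for AUD severity, motivation, risk-taking, insight and impulsivity".

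On the days before the scan, the protocol (Inpatient Lead-In Phase; 10-Day DIS Treatment) has patients discharged after the pre-DIS scan and first dose. They then attend four clinic visits, one every other day, with the post-DIS scan after the fourth. Alcohol use since the previous visit is asked about, and breath alcohol tested, at each of these visits. Drinking in this phase is foreseen: secondary aim 4 plans a subgroup comparison of neural effects if more than one third "of patients sample alcohol during the 10-day DIS treatment and thus experience the DIS alcohol reaction". The drinking-related grounds for removal are repeated heavy drinking (Criteria for Early Discontinuation) and persistent heavy drinking despite significant reaction symptoms (Minimizing the Risks of Disulfiram Treatment).

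On the days after the scan (30-Day DIS Treatment): "The first weekly visit will occur 2 days after the post-DIS MRI scan", and at each weekly visit staff "administer TLFB self-report of alcohol use over the previous 7 days".

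**The concern.** Aim 2 is a prospective claim: the scan comes first and relapse follows. For a patient who has already drunk during the outpatient 10-day phase, the predictor is measured after drinking resumed. If recent drinking, or the reaction it provoked, is related to VS activity at the scan, and if those who have already drunk are likelier to drink again, an association between the scan and the outcome can arise without VS activity foretelling any new relapse.

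The Background presents VS output during treatment as a predictor of relapse and says that a positive pilot signal will support larger studies. Those studies would be justified on an ambiguous finding. The non-treatment and placebo groups proposed for them would not settle the ambiguity, because it arises within treated patients.

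**Working it through.** **1. Can a pre-scan drinker enter Aim 2?** Yes. Eligibility for Aim 2 does not require abstinence up to the scan, and a lapse or lighter drinking is not a ground for removal. Any drink in the following 30 days then meets the definition of relapse.

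**2. Does anything in the model account for it?** The protocol adjusts for pre-DIS VS activity. That scan takes place on the day of discharge, before the first dose, so it cannot carry information about drinking that happens later. The SAP's five further covariates include no term for drinking in the 10-day phase.

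**3. Does secondary aim 4 cover it?** No. It compares neural effects and does not touch Aim 2. It also has a threshold: 25/3 = 8.33, so it runs only with 9 or more of 25. Up to 8 pre-scan drinkers would lead to no separate analysis.

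**4. How large could the effect be?** The documents give no rate of pre-scan drinking, relapse rate, alpha or effect size, so there is no stated figure to reproduce. A simulation shows direction only. All its inputs are assumptions:
- no true VS effect within either group;
- relapse 30% in patients abstinent to the scan, and 30%, 70% or 90% in those already drinking;
- post-DIS VS activity higher by 0, 0.5 or 1 SD in those already drinking;
- pre/post VS correlation 0.5;
- likelihood-ratio test at two-sided 0.05, 1,000 runs per setting;
- model with post- and pre-DIS VS activity only.

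Percentage of runs in which post-DIS VS activity was significant, with 25 patients and 36% (on average 9) already drinking:

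| Relapse if already drinking | VS shift (SD) | Protocol's Aim 2 model | Prior-drinking term added | Abstinent to scan only |
|---|---|---|---|---|
| 30% | 0 | 8.1 | 8.8 | 8.8 |
| 30% | 1 | 6.2 | 7.0 | 8.6 |
| 90% | 0 | 7.0 | 9.4 | 11.6 |
| 70% | 0.5 | 10.8 | 7.8 | 10.0 |
| 70% | 1 | 17.1 | 6.5 | 10.4 |
| 90% | 0.5 | 12.3 | 7.7 | 9.8 |
| 90% | 1 | 30.9 | 7.9 | 10.3 |

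The first three rows lack one or both links, and the protocol's model shows only the usual small-sample excess over 5%. The last four have both links. With 20% already drinking, the same four settings give 7.8%, 12.1%, 10.8% and 21.8% for the protocol's model. With 200 patients and 36%, which removes the small-sample excess, they give 31.5%, 77.0%, 57.7% and 98.1%, against 4.4% to 6.4% after adjustment or restriction.

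**5. Can 25 patients carry the SAP's model?** It has 2 scan terms + 5 covariates = 7 predictors. If 30% relapse (assumed), 25 × 0.30 = 7.5 events, about one per predictor. In 16 patients abstinent to the scan, 16 × 0.30 = 4.8 events. Any added or restricted analysis needs a shorter model.

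**6. The first Timeline Followback (TLFB).** Set the scan at day 0, so that the first weekly visit is day +2. Seven days before the visit day are −5 to +1, of which 5 precede the scan. Counting the visit day, they are −4 to +2, of which 4 precede the scan.

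**The case against.** Several points on the other side stand.

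- **Few such patients.** The Background says most patients taking disulfiram do not sample alcohol, and doses in the 10-day phase are observed. A reader might infer from secondary aim 4 that more than a third are expected to drink before the scan. The text does not support that: the third is a trigger for an analysis, not a forecast.
- **Temporal order is correct.** The scan precedes every outcome day, and predicting any use rather than first use is a legitimate choice of question. Under the protocol's own model VS output drives drinking, so an early lapse may itself result from the mechanism. Adjusting for it, or excluding those patients, could remove part of a true effect. This is why the all-patient analysis should stay.
- **The TLFB window.** A reader might infer that pre-scan drinks are counted as relapse because the first weekly TLFB reaches behind the scan. The outcome is confined to the 30-day period. Whether that period starts after the scan or at the visit 2 days later (the protocol says both), pre-scan days lie outside it. They would enter only if the first TLFB were scored whole, which no section says. Only a clarification is needed.
- **A pilot with stated limits.** The protocol acknowledges that it lacks control groups for important confounds. It does not name this one, and the remedy needs no control group.

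What the objection does not answer is that the plan gives no way to tell new relapse from continued drinking.

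**Conclusion.** The gap is real. Followed exactly, Aim 2 pools patients who relapse after the scan with patients who had already resumed drinking, and neither document separates them or adjusts for the difference. A positive result would then be ambiguous. It would be too strong to say that it is no evidence of prediction.

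The ambiguity requires two links, from pre-scan drinking to VS activity and from pre-scan drinking to later drinking. The documents make the first plausible, since secondary aim 4 asks whether experiencing the reaction has its own neural effects, but they quantify neither. The size is therefore unknown and may be small if few patients drink before the scan. The simulated rates (11% to 31% when 36% are already drinking and both links hold) rest wholly on assumed inputs. A reader might also take the share of relapses contributed by earlier drinkers as the bias. That share would depend on assumed counts and would say nothing about the VS coefficient.

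**What to change.** 1. Keep the all-patient Aim 2 analysis. Pre-specify one sensitivity analysis beside it: either add a single indicator for any alcohol use between the first disulfiram dose and the post-DIS scan, or restrict to patients with no such use. The indicator keeps all 25 patients and stayed at 7% to 9% in the simulation with 36% already drinking; restriction gave 9% to 12%.
2. Fit it with post- and pre-DIS VS activity only, plus the indicator if that version is chosen.
3. Define pre-scan use from self-report and breath results at the four visits, with urine ethyl glucuronide (EtG) where collected. The 10-Day DIS Treatment text has EtG at every visit, while the table under Blood and other Biological Samples, as it reads in the extracted text, shows it only at the final visit of that phase. Reconcile the two. No rule on carry-over of EtG into the outcome window is proposed, because the documents give no detection times.
4. Describe the result as predicting new relapse only if the sensitivity analysis agrees with the all-patient one.
5. As a clarification, state that the outcome window starts the day after the post-DIS scan, so that earlier days in the first TLFB are not counted.

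The cost is a few sentences in Aim 2 and the SAP, with no new visits and no change to treatment. The downside is an imprecise sensitivity estimate, which should be reported with its confidence interval.

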## Background, Significance and Rationale

### Background, Significance and Rationale

Disulfiram (DIS) is one of the oldest, most effective, and most commonly used treatments for alcohol use disorder (AUD)(1). DIS is a medication that causes a highly aversive visceral reaction if alcohol is consumed while it is being taken (the DIS-alcohol reaction). Most patients who take DIS do not sample alcohol while taking it (2) indicating that the experience of the DIS-alcohol reaction is not necessary for behavior change, but instead that the mere expectancy or threat of this aversive reaction, i.e. subjective risk, is sufficient to induce behavior change. Here, we are interested in examining the neural underpinnings of this risk-based behavior change mechanism.

The fact that some patients do drink during DIS treatment despite the subjective risk of the DIS-alcohol reaction suggests a limitation of efficacy rooted in a failure of risk-based decision processes. There is a large body of evidence that AUD and other addictive disorders are associated with deficits in risk-based decision making and its neural substrates(3, 4). By understanding the neural mechanisms that mediate behavior change (and the failure of behavior change) during DIS treatment, it may be possible to improve the efficacy of DIS and other treatments that depend upon an awareness of risks by identifying targets for biologically-based augmentation therapies can be combined with such therapies. Such risk-based therapies include DIS, as well as behavioral treatments such as Motivational Interviewing and Contingency Management.

Furthermore, reduction in alcohol use as a result of a shift in subjective risk is likely to play an important role in behavior change outside of treatment.

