Previous work by the PI(5) and others(6) has provided circumstantial evidence that excitatory inputs from the insula and the ventromedial prefrontal cortex (VMPFC) into the ventral striatum (VS) drive a specific “goal-directed” form of drug and alcohol seeking that is engaged when there is a high level of subjective risk. The PI has also shown that cue-induced alcohol craving can be reduced by thinking about risks of alcohol use(7). In cigarette smokers, this risk-based form of cognitive regulation of craving is mediated by negative functional connectivity between the dorsolateral prefrontal cortex (DLPFC) and the VS(8). Furthermore, effective AUD treatments consistently down-modulate cue-induced activity in the VS(9), suggesting an important role for this region in therapeutic behavior change.

Based upon this prior work, we propose that DIS treatment - specifically, the mere belief that drinking will cause the DIS-alcohol reaction - changes behavior by promoting a goal-directed mode of cue-induced alcohol seeking. In this mode, the output of the VS is governed by a balance between (1) excitatory inputs from the insula and the VMPFC that together represent the incentive value of alcohol, and (2) inhibitory inputs from the DLPFC that down-modulate VS output according to the perceived unpleasantness and likelihood of the DIS-alcohol reaction. The resulting VS output determines the magnitude of cue-induced craving during DIS treatment, and predicts the likelihood of relapse during DIS treatment.

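### Secondary aim 4 claims to settle whether experiencing the disulfiram reaction differs neurally from expecting it, but patients select themselves into the comparison; the result can only be associational

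*Protocol*

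**What the plan says.** The analysis is item (4) of the Secondary Aims (Protocol, Specific Aims and Hypotheses). It is triggered if more than one third of "patients sample alcohol during the 10-day DIS treatment and thus experience the DIS alcohol reaction". In that case, "we will perform a subgroup analysis comparing how the neural effects of DIS treatment in such patients differ from patients" who did not sample. (The text names disulfiram as the thing not sampled; I read it as alcohol.) The inference promised is: "This will allow us to determine whether the neural effects of actually experiencing the DIS-alcohol reaction are different from the effects of mere expectation".

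The neural effects of treatment are, under Aim 1, changes from the pre- to the post-disulfiram scan. The SAP models time-point in the same way, so I take the planned contrast to be pre-to-post change in samplers against pre-to-post change in non-samplers.

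The Background section gives the protocol's account of why patients drink on disulfiram. The fact that some do so "suggests a limitation of efficacy rooted in a failure of risk-based decision processes". Insula and ventromedial prefrontal inputs to the VS are said to drive a "form of drug and alcohol seeking that is engaged when there is a high level of subjective risk". On the VS itself: "The resulting VS output determines the magnitude of cue-induced craving during DIS treatment, and predicts the likelihood of relapse during DIS treatment".

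The SAP contains no sampler analysis. Its listed covariates belong to the logistic model of drinking during one month of disulfiram.

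**The concern.** Nobody is assigned to sample. Patients enter willing to attempt complete abstinence (inclusion criterion 8) and are warned repeatedly about the reaction. Those who drink anyway form a self-selected group defined after baseline. The post-disulfiram scan comes at the end of the 10-day phase, after any such drinking.

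A difference in neural change between the groups therefore has at least two explanations: the reaction altered the brain response, or the brain response (or something that goes with it) led the patient to drink. The protocol's own theory makes the second a live possibility. The limitations paragraph in the Background section names the missing no-treatment and placebo groups but not this selection, and those groups would not randomise sampling either.

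At stake is what may be concluded. If the trigger is met and the test is positive, the protocol's wording licenses the report that experience and expectation have different neural effects, when selection alone could have produced the result.

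**Working it through.** **No figure to reproduce.** The documents give no power, error rate, effect size or sampling rate for this analysis. The calculations below illustrate the design argument and rest on stated assumptions.

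**Group sizes.** Planned completers: 25 (Specific Aims and Hypotheses). More than one third means more than 25/3 = 8.33, so at least 9 samplers against at most 16 non-samplers.

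**Selection model (assumed).** Pre- and post-disulfiram VS activity are standard normal with correlation 0.4-0.6. The reaction has no effect. The chance of sampling follows logit(p) = logit(0.33) + ln(3) × z, where z is pre-disulfiram activity, post-disulfiram activity, or the standardised change. An average patient has odds of 0.33/0.67, about 0.5. One SD higher gives 0.5 × 3 = 1.5, a probability of 60%. One SD lower gives 0.5/3 = 0.17, a probability of about 14%. Trials with at least 9 samplers are kept and tested at two-sided 0.05.

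| Selection acts on | Planned change comparison significant | Post-disulfiram activity adjusted for pre-disulfiram activity, significant |
|---|---|---|
| Pre-disulfiram VS | about 16-22% | about 5% |
| Post-disulfiram VS | about 16-22% | about 44-54% |
| The change itself | about 65% | about 47-54% |

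With an odds ratio of 1 (no selection), all comparisons return about 5%. With an odds ratio of 2 on post-disulfiram activity (run at 36% sampling for an average patient), the change comparison is significant in 10-13%.

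**A second selection model.** Let the 9 of 25 patients with the highest latent propensity sample, and let propensity correlate r with the VS change. The spurious group difference is about 1.57 × r in SD units:

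- r = 0.3: 1.57 × 0.3 = 0.47 SD, significant in 20% of trials.
- r = 0.5: 1.57 × 0.5 = 0.78 SD, significant in 49%.
- r = 0: no difference, significant in 4.9%.

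The two models need not agree, because they describe different selection. Both show a test well above its nominal level with no effect of the reaction.

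**Would a pre-disulfiram comparison reveal the selection?** At an odds ratio of 3 it is significant in about 63% of trials if selection is on pre-disulfiram activity, but in only 13-24% if selection is on post-disulfiram activity. A null result there would be common even when selection is strong.

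**Chance that the analysis is run.** The binomial probability of 9 or more samplers among 25 is 4.7% at a true sampling rate of 20%, 15% at 25%, 46% at 33% and 73% at 40%.

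**The case against.** The planned contrast is already a within-patient change, which removes stable differences between samplers and non-samplers. The analysis is a conditional fourth secondary aim in a self-described pilot that concedes it lacks controls for important confounds. The Background section says most patients on disulfiram do not sample alcohol, so the trigger may never be met. No primary aim depends on the result, and the odds ratio, correlation and sampling rate above are all assumed.

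Most of this stands, and it limits severity. It does not rescue the claim. Change scores remove stable differences but not selection on the change itself, nor the regression to the mean that follows selection on activity at one scan. The pilot caveat does not reach self-selection.

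Three stronger readings are tempting, and none should be adopted.

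- **A false-positive rate near 63%.** A reader could compute that figure for selection on post-disulfiram activity at an odds ratio of 3, but it belongs to a comparison of post-disulfiram activity alone. The protocol compares treatment effects, that is, change.
- **Aim 2 already predicts a positive result.** Aim 2 concerns relapse in the 30 days after the post-disulfiram scan, whereas sampling happens before it. The general model in the Background section makes selection plausible; Aim 2 does not state it.
- **The defect is a missing baseline covariate.** Adjustment restores about 5% only when selection is on pre-disulfiram activity. Under selection on post-disulfiram activity it raises false positives from 16-22% to 44-54%.

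**Conclusion.** The concern holds as a point about inference. The comparison can describe an association between sampling and neural change. It cannot determine whether experiencing the reaction differs from expecting it, because membership of the groups is self-selected, precedes the second scan and, on the protocol's own account, is driven by neural and decision processes. That conclusion needs no simulation.

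The size is illustrative: with no true effect, about 16-22% of trials would be significant if selection is on VS activity at either scan, and about 65% if it is on the change. This assumes an odds ratio of 3 per SD, a pre/post correlation of 0.4-0.6, 33% sampling at average activity, and a single VS measure, although the aim itself is not limited to the VS. Weaker selection gives smaller figures.

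Severity is minor. The wording should still change, because it governs what the trial may report if the analysis is run.

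**What to change.** Replace the final sentence of secondary aim 4 with:

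> This exploratory comparison describes the association between sampling and neural change; it cannot separate the effect of the reaction from differences that led patients to sample.

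Keep the pre-to-post change contrast. If the pre-disulfiram group difference and a model of post-disulfiram activity adjusted for pre-disulfiram activity are reported, label both as sensitivity analyses. State that the adjusted model corrects only selection on pre-disulfiram activity and can do worse than the change contrast otherwise, and that a null pre-disulfiram difference does not rule out selection.

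The change needs no new data or visits. Its cost is a less ambitious secondary claim.
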